**3.1.6 Intervention. a) Intervention group.** The goal of our breastfeeding intervention is consistent with AAP and ACOG guidelines: exclusive breastfeeding for the first 6 months of life, with continued breastfeeding as complementary foods are introduced through the infant's first year of life, or longer as mutually desired by the mother and her infant. Participant will complete 13 one-hour intervention visits: 5 during pregnancy and 8 in postpartum. Prenatal breastfeeding education will be weekly for 5 weeks at the PI's lab. After delivery, we will meet the participant at her home in 1 week, 2 weeks, and 1 month; and then monthly at the PI's lab until 6 months postpartum. Participants will receive \$15/visit compensation. Our team has rich experience in running behavioral interventions for the target population, for instance, most participants (73.9%) in the PI's smoking cessation study have completed 35 one-hour prenatal intervention visits and 12 monthly 1.5-hour postpartum follow-up visits with similar compensation (\$15/hour). The breastfeeding intervention components will include prenatal breastfeeding education, postnatal lactation counseling, family/peer/employer support, contingent financial incentives, and early limited formula milk via syringe (optional for at-risk infants).

**Component #1 - Prenatal breastfeeding education:** To maximize the effect, breastfeeding education will start in late pregnancy (28+ weeks) when the mother and family seriously plan on infant feeding. The breastfeeding plan will cover breastfeeding on demand, pain management, skin-to-skin contact, breastfeeding tips after cesarean section, lactation support, breastfeeding away from home, breast pump, maternity leave, and back-to-work scheduling. Educational approaches will include readings with quizzes (\$2 reward if passed), discussion, video, demonstration and practice with a baby simulator. Prenatal breastfeeding education will be delivered in a group with 6 pairs of participants and their family supporters per group. Physical examination of breasts and nipples will be conducted by a certified lactation counselor (CLC) to address potential issues including infectious conditions, dermatitis, breast masses, breast surgery, and flat or inverted nipples.

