**Component# 2 - Postnatal lactation counseling:** A part-time CLC will be hired to provide timely and individualized postnatal lactation counseling. She will monitor each participant's breastfeeding progress, help them initiate breastfeeding immediately after delivery, correct myths and flaws, answer questions, and offer suggestions and tips to solve potential problems. Besides face-to-face meetings, text messages and phone calls will also be used to provide timely assistance of lactation practice and routine checking of feeding status.

**Component #3 - Family/Peer/Employer support:** The participant will nominate a family supporter for her breastfeeding. The family supporter will receive our training for skills in supporting the participant's decision and effort to breastfeed. Other family members will also receive a breastfeeding support booklet. The PI has successful experience of training 16 family supporters for our Pregnancy and Smoking Cessation Study. In addition, we will encourage participants to attend Buffalo's Baby Cafés (6 sites), a breastfeeding drop-in support group, to seek further support from lactation counselors and other breastfeeding mothers (peers). Particularly, the PI has been collaborating with one of these sites, the Durham's Central City Baby Café (see **Letter of Support**). This Baby Café has been helping 214 of 221 mothers (96.8%) to breastfeed successfully since 2013. A booklet on benefits of breastfeeding for business, how to support a nursing mother in workplace, laws and policies of promoting breastfeeding will be available to the participant's employer.

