**Component #4 - Contingent financial incentives:** Participants will receive incentives for breastfeeding if they are able to nurse or to provide milk by pumping in the presence of a female research staff. In the Co-I [name] effective intervention (e.g., 72% breastfeeding rate at 6 months postpartum vs. 0% usual care), contingent incentives start at \$20 at the end of first month and increase by \$10 every month until the end of 6 months postpartum. We will adapt this incentive schedule for the proposed project by adding two home visits in week 1 and week 2 postpartum for breastfeeding consultation with \$20 incentive for breastfeeding, given that the first month postpartum is critical to address high risk of breastfeeding discontinuation and smoking relapse. The family supporter will also receive \$10 incentive/month if the participant is still breastfeeding.

**Component #5 - Early limited formula milk (ELF) via syringe:** This component is optional and is only reserved for at-risk infants with 5% or more birth weight loss within the first 2 days of life when the mother decides to add formula. The goal of ELF is to ensure supplemental use of formula to help the at-risk infant grow but will not interrupt the success of breastfeeding. Specifically, the mother should always breastfeed the infant first. If needed, a limited amount (10.0 mL or less) of formula milk is then complemented. The formula milk is administered via syringe rather than baby bottles, which can prevent nipple confusion. ELF will be discontinued once breast milk can meet the infant's need, usually within 2 weeks. ELF has been shown to increase exclusive breastfeeding rate (79% vs. 42% usual care) at 3 months postpartum for at-risk infants.

**b) Control Group.** Participants in the control group will receive a brief pamphlet on the benefits and skills of breastfeeding. They will complete the same frequency of study visits as the intervention group to monitor their feeding plan/practice with a fixed compensation (\$15/visit), regardless of feeding practice.

**c) Fidelity and quality control.** Step-by-step instructions will be used for each visit. The PI will train all research staff. Evaluation will be conducted via exams and trial runs before their interacting with participants. All visits will be audio-recorded for quality assurance and 20% of audio files will be reviewed by the PI.

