**Comments.** We decided not to include any education or intervention directly targeting on smoking relapse. This will allow us to test the independent effect of breastfeeding promotion on smoking relapse.

**3.1.7 Follow-up.** To evaluate sustainability of the effects of breastfeeding promotion on smoking relapse, we will follow participants and infants in 9 months postpartum (i.e., 3 months after breastfeeding intervention ends).

**3.1.8 Outcome measures.** The key outcome measures include timing of postpartum smoking relapse (primary) and breastfeeding duration (secondary) derived from data repeatedly collected throughout the study (**Table 1**). Outcomes will be assessed by graduate research assistants who are blinded to group assignments.

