*Maternal negative affect.* Maternal negative affect will be measured at enrollment and all postpartum visits using the Positive and Negative Affect Schedule (PANAS). The 10 items on negative affect include being distressed, upset, guilty, ashamed, hostile, irritable, nervous, jittery, scared, and afraid. Participants will rate their experience of each particular emotion in the past few weeks. With this time frame, its Cronbach's alpha was 0.87 and test-retest reliability was 0.48. In addition, we will measure maternal anxiety with the State-Trait Anxiety Inventory and postpartum depression with the Edinburgh Postnatal Depression Scale.

**3.1.10 Covariates.** We consider partner smoking, maternal secondhand smoke exposure, education, household income, health motivation, perceived social support, as covariates. They may confound our results and will be controlled in data analysis if not comparable between intervention and control groups.

**3.1.11 Economic costs.** We will collect information on intervention (not research and development) costs such as personnel, recruitment, materials, compensation, incentives, and transportation. We will include outcome costs for formula, medical care of NICU stay and sick child visits, and parental absenteeism for infant illness.

**3.1.12 Statistical Analysis.** *Specific Aim 1 (Breastfeeding promotion and postpartum smoking relapse).* The timing of postpartum smoking relapse (outcome) will be analyzed with Cox regression model by including group assignment (intervention vs control), smoking status (1=smoking, 0=non-smoking), the observed time, and significant covariates. The proportional hazard ratio of postpartum smoking relapse between two groups will be calculated. We will estimate Kaplan-Meier survival curves to visually compare smoking trajectories. Intent-to-treat analysis will be used with all randomized participants being included in their originally assigned groups. Dropouts, losses to follow-up, fetal deaths, and miscarriages will be coded as missing data on smoking status. If missing data on smoking status is more than 20%, we will run pattern mixture models and sensitivity analyses. A supplemental analysis will be run to examine *prenatal* smoking relapse during pregnancy.

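### Smoking status to month 6 is collected only at intervention visits; breastfeeding-contingent pay in one arm could make losses selective, and the 20% missing-data trigger could overlook it

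*Combined protocol and SAP*

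**What the plan says.** **Visits.** Section 3.1.6 a) states: "Participant will complete 13 one-hour intervention visits: 5 during pregnancy and 8 in postpartum". The eight postpartum visits fall at weeks 1 and 2 and months 1 to 6. Section 3.1.8 says that the outcomes are "derived from data repeatedly collected throughout the study", and Table 1 places smoking status at those eight visits and at month 9. Month 9 is the only postpartum assessment outside the intervention (3.1.7).

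**Pay.** Intervention participants receive $"15/visit compensation", with no feeding condition. Controls attend equally often for a fixed $15, "regardless of feeding practice". Component #4 adds, for the intervention arm only: "Participants will receive incentives for breastfeeding if they are able to nurse or to provide milk by pumping" in front of staff. The amount is $20 at month 1, rising by $10 a month to month 6, with $20 for the added week 1 and week 2 visits. Her supporter receives $10 a month while she breastfeeds.

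**Contact.** Component #2, for the intervention arm, says that "text messages and phone calls will also be used to provide timely assistance of lactation practice and routine checking of feeding status". Nothing comparable is described for controls.

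**Missing data.** Section 3.1.12 says: "Dropouts, losses to follow-up, fetal deaths, and miscarriages will be coded as missing data on smoking status". Pattern-mixture models and sensitivity analyses follow only if more than 20% of smoking status is missing, with no rule by arm. Section 3.2 expects 20% attrition and provides for calling three named contacts when touch with a participant is lost.

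**The concern.** A woman who stops coming to intervention visits also stops supplying outcome data, unless she returns at month 9. In the intervention arm, the reward for coming depends on whether she still breastfeeds; in the control arm it does not. Section 1 cites a 30-60% lower relapse risk in breastfeeding mothers. If intervention women who have stopped breastfeeding attend less, that arm loses follow-up on its higher-risk members, and a Cox model that treats them as ordinary censored observations understates relapse there.

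This would be informative censoring produced partly by the trial's own procedures. Including every randomised woman in her assigned group does not recover a relapse that nobody recorded. The pilot is meant to inform efficacy and to support a larger application, so even a modest bias would carry forward.

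No step in the plan addresses outcome collection from a reachable woman who has stopped attending. The three-contact step covers lost contact. The daily smoking calendar in 3.1.8 is kept by the participant, and no route is given for obtaining it from a non-attender.

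**Working it through.** The plan gives no figure for loss by feeding status, so there is none to reproduce. The checks below use its payments, its relapse rates and labelled assumptions.

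**1. Value of a visit.** Reading the $20 as paid at both week 1 and week 2:
- Contingent pay: 20 + 20 + 20 + 30 + 40 + 50 + 60 + 70 = $310, on top of 8 × 15 = $120 base pay.
- Month 6: 15 + 70 = $85 for a breastfeeding intervention mother; $15 for one who has stopped; $15 for any control.
- Month 5, adding the $40 feeding session of 3.1.9, which accepts any feeding method: 15 + 60 + 40 = $115 against 15 + 40 = $55 for a stopper or a control.

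**2. The trigger.** 20% of 60 is 12 women. Twelve losses all in the intervention arm would be 12/30 = 40% of that arm, yet would not exceed 20% overall.

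**3. Loss at weaning, with no true effect of assignment (simulation).** Assumptions, the same in both arms unless stated:
- Exponential feeding duration with mean 4 months.
- Relapse hazard 0.088 per month while feeding and 0.16 after. The ratio is 0.55, matching the 45% protection in 3.1.13.
- Relapse by 9 months is then about 69%, close to the plan's 70%.
- Controls are lost at random at 0.03 per month (about 15% lost). Intervention women leave only at weaning, with the probability shown.

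| Leave at weaning | Lost, intervention | Lost, overall | Cox HR |
|---|---|---|---|
| 30% | 21% | 18% | about 0.96 |
| 40% | 28% | 22% | about 0.94 |
| 50% | 35% | 25% | about 0.92 |

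These come from large runs (60,000 or more per arm), which agree to about 0.01. The first row stays under the 20% trigger; the other two exceed it.

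**4. Month-6 illustration, with no true effect.** Inputs: 45% relapse in both arms (3.1.13); 72% of the intervention arm still breastfeeding (the earlier trial cited in section 1); relative risk 0.55.
- Relapse in stoppers: 0.45 / (0.72 × 0.55 + 0.28) = 0.666. In breastfeeders: 0.55 × 0.666 = 0.366.
- Half of the stoppers lost (14% of the arm, 7% of the trial): (0.72 × 0.366 + 0.14 × 0.666) / 0.86 = 0.415. Apparent HR ≈ ln(1 − 0.415) / ln(1 − 0.45) = 0.90.
- All stoppers lost (28% of the arm, 14% of the trial): observed 0.366, HR about 0.76.
- With relative risk 0.70 to 0.40 (the cited 30-60%), half lost gives HR 0.94 to 0.84.

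This removes lost women entirely, whereas a Cox model keeps their time up to leaving, so it is cruder than step 3.

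**5. Opposite direction.** If two relapsing controls of 30 are lost, observed control relapse is (13.5 − 2) / 28 = 0.411. Set against the 0.415 from step 4, HR ≈ ln(0.585) / ln(0.589) = 1.01. The bias is cancelled. With no loss in the intervention arm, it becomes ln(0.55) / ln(0.589) = 1.13, against the intervention.

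**The case against.** The strongest reply is that the plan treats the arms more evenly than a quick reading suggests, and that any bias is hypothetical and small.

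- **Pay.** A reader might infer that attendance pay itself depends on breastfeeding, so that stoppers are penalised. The documents do not support that. Base pay is $15 in both arms, so a woman who has stopped gets what a control gets. The $40 sessions at months 1, 3 and 5 are open to any feeding method, and the week 1, week 2 and month 1 visits are at home. This stands: the mechanism is extra retention of breastfeeders, and month 6 shows the gap at its starkest.
- **Texts and calls.** Nothing says that they end at weaning, and they could help to keep intervention women in the study. This stands.
- **Planned handling.** Sensitivity analyses are planned above 20% missing, and two of the three simulated scenarios would reach that level. This stands for heavy loss. It does not answer the cases below 20%, or loss concentrated in one arm.
- **Size.** With 45% to 70% relapse in 30 per arm (13.5 to 21 events), the standard error of the log hazard ratio is about √(2/21) = 0.31 to √(2/13.5) = 0.38. A hazard ratio of 0.92 is a shift of 0.08, well within that noise. The plan's 70% against 39% implies ln(0.61)/ln(0.30) = 0.41. This stands: the bias alone would not produce the hoped-for effect.
- **Control losses.** Controls' visits also monitor feeding, and relapsing controls may leave too. This stands, as step 5 shows.

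**Conclusion.** The concern holds as a risk in the design. Outcome and intervention visits coincide through month 6, breastfeeding-contingent pay is in one arm only, dropouts become missing, and the missing-data check is overall-only, with a threshold equal to the expected attrition. Selective loss of stoppers would then move the hazard ratio towards benefit, possibly without any check being run.

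The size rests on assumed loss rates: about 0.96 to 0.92 for 30% to 50% leaving at weaning, and about 0.90 (0.94 to 0.84 across the cited risk range) if half of the stoppers at month 6 are lost.

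Two stronger readings are tempting but unsupported. The documents do not show that stoppers will be lost; they give no retention figures by feeding status. Nor is it shown that the bias arises when overall attrition is equal between arms: the simulated scenarios have 21% to 35% lost against about 15%. The direction also depends on control-arm losses, which could shrink or reverse it. The case for acting is that unrecorded relapse dates cannot be recovered by analysis and the remedy is cheap.

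**What to change.** In 3.1.7-3.1.8, state that stopping the intervention or missing a visit does not end outcome collection. In both arms, after any missed visit and at months 6 and 9 for non-attenders, existing staff phone or text for smoking status, relapse date (read from the calendar) and feeding status. Pay the same small amount in both arms whatever the feeding, set below the $15 visit payment so that it does not discourage attendance. Request a cotinine sample if she agrees. The breastfeeding incentive is unchanged.

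In 3.1.12, use these dates in the primary Cox analysis and flag those without cotinine. Report missingness by arm and by feeding status, and run the missing-data sensitivity analyses regardless of the 20% trigger.

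Cost: a protocol paragraph, a short script, staff time and the payments. As an upper bound, if 20% of 60 × 9 = 540 postpartum assessments were missed (an assumption), that is 108 contacts at under $15, or less than $1,620. Downsides: some relapse dates will lack cotinine confirmation, and there is a small risk that phone contact replaces visits.

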**3.1.3 Screening.** Interested participants will sign consent forms and complete a survey on socio-demographics, pregnancy, medical history, mental health, history and status of cigarette smoking, use of other tobacco or nicotine products, alcohol and other substance use, and infant feeding plan. Those who had quit smoking cigarettes within 3 months before or during this pregnancy will be invited for lab screening to verify their current non-smoking status by urine cotinine (metabolite of nicotine). Collateral reports (e.g., from employer, partner, friend, or relative) or medical records will be used to verify their previous smoking history. Eligible participants

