**Figure 1. Conceptual Model for Breastfeeding and Smoking Abstinence\***

\* Other hormonal mechanisms, such as progesterone, estrogen, ACTH, cortisol, and tetraiodothyronine (T4), will be included in the larger R01 grant.

must be at 28 weeks of pregnancy or earlier to ensure adequate time for prenatal breastfeeding intervention. Exclusion criteria are teen pregnancy (<18 y); current use of other tobacco or nicotine products; medical conditions contraindicating breastfeeding such as HIV infection, active tuberculosis, and breast removal; current heavy drinking (more than 2 drinks a day); current use of other psychoactive substances; being strongly against breastfeeding; and non-English speakers. To increase the possibility to obtain a representative sample of the generable population, the study will be advertised as a program to promote healthy infant feeding among pregnant women without requiring breastfeeding intention or mentioning smoking relapse prevention. We will not exclude women without current intention to breastfeed (28.6% in our pilot survey), unless they are strongly against breastfeeding (4.8%). Similarly, we will not exclude women who plan to relapse after delivery (0% in our pilot survey), as our breastfeeding promotion may motivate them to maintain abstinent for a longer period especially if they know tobacco metabolites are concentrated in breast milk.

**3.1.4 Pre-test visit.** During this visit, we will measure the participant's urine cotinine, height, and body weight. Participants will complete a survey on smoking temptations, nicotine dependence before quitting, smoking cessation history, self-efficacy to maintain smoking abstinence, smoking environment including partner smoking behaviors, breast health, breastfeeding knowledge, breastfeeding history, relationship with partner and other family members, social network, stress, negative affect, physical activity, sleep, and diet.

**3.1.5 Randomization.** At 28 weeks of pregnancy, eligible participants will be randomized into either the intervention group (N=30) or the control group (N=30) using a sequence of random numbers in blocks of 2, which can ensure equal or close numbers of participants between the two groups throughout the project.

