*Specific Aim 2 (Mediation analyses on mechanisms).* We will use dynamic path analysis to examine the mechanisms through which breastfeeding reduces smoking relapse. The dynamic path analysis includes simultaneous fitting of the Aalen additive hazards model (the R package 'timereg') and ordinary path analysis (PROC TCALIS in SAS). It fits our survival data with internal time-dependent mediators (e.g., oxytocin or prolactin) and a counting process as the outcome (i.e., smoking relapse). Hormonal baseline level and response to infant feeding (oxytocin or prolactin) will be included into the model as independent mediators. We will estimate the direct, indirect (through one or multiple mediators), and total effects of breastfeeding on smoking relapse (**Figure 1**). The PI has sufficient experience in mediation analysis.

**3.1.13 Sample size.** According to the literature, we estimate 45% rate of smoking relapse by 6 months postpartum in the control group. Assuming 45% protection effect of breastfeeding against postpartum smoking relapse, we estimate 25% (45%\*[1-45%]) rate of smoking relapse by 6 months postpartum in the intervention group. The corresponding sample size is 98 per group with type 1 error  $\alpha$  of 0.05 and power  $1-\beta$  of 0.8 to detect significant difference in smoking relapse between two groups in the larger R01 project. If 9-month postpartum smoking relapse rates (70% control vs 39% intervention) are used, the corresponding sample size is 46 per group. Therefore, 30 participants per group for this pilot study should provide sufficient sample size to test feasibility and efficacy as well as provide preliminary data regarding mediators and cost-effectiveness.

**3.2 Potential Problems & Alternative Strategies.** A potential challenge for the proposed project is to recruit a sufficient number of pregnant ex-smokers. If significant delay is observed, we will expand recruitment areas, use direct mailing, and advertise in local media. Another potential problem is attrition during intervention and follow-up periods. We expect 20% attrition rate due to dropouts, losses to follow-up, miscarriages, and fetal deaths. If we lose contact, we will reach out to the 3 people that have close relationship with the participant indicated at enrollment. We will recruit more participants to ensure sufficient statistical power if attrition is high.

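### The secondary outcome, breastfeeding duration, has no between-arm analysis in section 3.1.12, and the covariate rule in 3.1.10 leaves out its own baseline value, breastfeeding intention at enrolment

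*Combined protocol and SAP*

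**What the plan says.** Section 3.1.8 sets the two key outcomes: "The key outcome measures include timing of postpartum smoking relapse (primary) and breastfeeding duration (secondary"). Table 1 schedules breastfeeding status at nine postpartum visits, from week 1 to month 9, and places breastfeeding intention in the enrolment cell of the same row.

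Related baseline data are collected before randomisation. Screening (3.1.3) covers "alcohol and other substance use, and infant feeding plan", and the pre-test visit (3.1.4) covers "breast health, breastfeeding knowledge, breastfeeding history, relationship with partner and other family members".

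The covariate list in 3.1.10 begins "We consider partner smoking, maternal secondhand smoke exposure, education, household income, health motivation" and ends with perceived social support. Its six variables include neither breastfeeding intention nor breastfeeding history. They "will be controlled in data analysis if not comparable between intervention and control groups".

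Section 3.1.12 has two parts. For Aim 1, "The timing of postpartum smoking relapse (outcome) will be analyzed with Cox regression model by including group assignment" and other terms. Aim 2 is a path analysis "to examine the mechanisms through which breastfeeding reduces smoking relapse", with breastfeeding as the exposure and relapse as the outcome.

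On follow-up, 3.1.7 says "we will follow participants and infants in 9 months postpartum". The intervention goal in 3.1.6 is breastfeeding through the first year or beyond.

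**The concern.** Whether the intervention prolonged breastfeeding is the first link in the trial's causal chain, and it is the named secondary outcome. Section 3.1.12 leaves the test, the effect measure, the censoring rule and the handling of never-initiators to be chosen after the data are seen. Aim 2 does not fill the gap, because it starts from breastfeeding and not from the randomised arm.

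The covariate rule adds a second weakness. It checks six listed variables and adjusts only for those that look unbalanced. Enrolment intention is not on the list, so it would be neither checked nor adjusted for, although Table 1 treats it as the pre-test value of this outcome. Section 3.1.3 deliberately admits women without intention to breastfeed (28.6% in the pilot survey), and 3.1.5 states no stratification. If intention predicts duration, the plan gives up precision that its own data could supply.

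**Working it through.** **The plan's own figures.** There is no calculation for breastfeeding duration. The only sample sizes, in 3.1.13, concern relapse. They reproduce with the two-sided two-proportion formula (α 0.05, power 0.80) and continuity correction:

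- n = [1.96·√(2p̄(1−p̄)) + 0.842·√(p₁(1−p₁)+p₂(1−p₂))]² / d², then n′ = (n/4)·[1+√(1+4/(n·d))]².
- 45% vs 25%: n = 89 after rounding up, n′ = 98, as stated.
- 70% vs 39%: n = 40 after rounding up, n′ = 46, as stated.

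Nothing below changes these.

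**Chance imbalance in intention.** Inputs: 28.6% without intention (3.1.3) and 30 per arm (3.1.5), with independent binomial counts as an approximation.

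- SD of the difference = √(2 × 0.286 × 0.714 / 30) = 0.117, or 11.7 points.
- P(difference of 4 or more women, 13 points) = 0.316.
- P(difference of 6 or more women, 20 points) = 0.115.

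**Power with and without adjustment.** The documents give neither the prognostic strength of intention nor a target effect on duration, so both are assumed and shown as a range. Setting: 30 per arm, exponential weaning, control median 2 months, arm hazard ratio (HR) 0.5, 20% dropout, cut-off at 9 months, Cox model, simulated trials.

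| HR of stopping, no intention vs intention | Unadjusted | Adjusted |
|---|---|---|
| 1 | 67% | 67% |
| 2 | 63% | 68% |
| 3 | 57% | 68% |
| 4 | 53% | 66% |

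A repeat run gave 62% to 67% at HR 2 and 50% to 66% at HR 4, so the gains carry simulation error of a few points. Type I error was 5–6%.

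**Larger effects.** Sections 1 and 3.1.6 cite 72% vs 0% breastfeeding at 6 months for the intervention being adapted.

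- Weaning rate in the intervention arm = −ln(0.72)/6 = 0.0548 per month.
- Control rate at a median of 2 months = ln 2/2 = 0.347 per month.
- Implied arm HR = 0.0548/0.347 ≈ 0.16. Power is then essentially 100% with or without adjustment.
- At the intermediate HR of 0.3, adjustment moves power from 97% to 98% (no-intention HR 2) and from 89% to 97% (no-intention HR 4).

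**Censoring at 9 months.**

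- At 72% at 6 months, the share still breastfeeding at 9 months = 0.72^(9/6) = 0.61.
- At arm HR 0.5, the shares are exp(−0.173 × 9) = 21% in the intervention arm and exp(−0.347 × 9) = 4% in the control arm, before dropout.
- An exponential mean cut at 9 months is (1 − e^(−9λ))/λ. At HR 0.5 this gives 4.56 vs 2.76 months, a difference of 1.80. The uncut means are 5.77 and 2.89, a difference of 2.89.
- Means of durations cut at 9 months would therefore understate the difference by about 38% (1 − 1.80/2.89).

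**The case against.** Several objections have force.

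- **The gain rests on assumptions.** No section says how strongly intention predicts duration. If it does not, adjustment gains nothing. At the effect size the plan itself cites, the covariate hardly matters. Both points stand, and the range above reflects them. The earlier study was in low-income mothers, not specifically ex-smokers, so a smaller effect remains possible.
- **The 28.6% is soft.** If it is 6 of the 21 pregnant women in the pilot survey, the exact 95% interval is about 11% to 52%. If the 4.8% strongly against breastfeeding, who are excluded, fall within it, the eligible share is nearer 25%, and the two imbalance probabilities fall to about 30% and 10%. This stands.
- **The covariate list was written for possible confounders of relapse.** Leaving a variable out of it, or not stratifying a 60-woman pilot on it, is not an error in itself. This stands: the omission costs precision only.

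A reader might infer more than the documents support:

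- *That the plan uses a biased comparison of means.* No section proposes one; the plan is silent on the method.
- *That leaving out intention biases the arm comparison.* Randomisation protects it, and the simulated Type I error stays near 5%.
- *That a null relapse result could not be interpreted.* Breastfeeding status is collected in both arms at nine postpartum visits and visually verified (Table 1, 3.1.8). Simple proportions breastfeeding at month 6 by arm would still show whether promotion worked.

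**Conclusion.** The point holds as a worthwhile improvement, not as a flaw that invalidates the trial. The named secondary outcome has no between-arm analysis and no censoring rule, and the covariate rule passes over a baseline value the trial already collects.

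The benefit of adjustment is precision. With 30 per arm, a control median of 2 months and an arm HR of 0.5, it is 0 points of power if intention is not prognostic, about 5 at a no-intention HR of 2, and about 10 to 15 at 3 to 4. It is essentially nil at 72% vs 0%. The need for a time-to-event method runs the other way: the larger the effect, the heavier the censoring in the intervention arm, reaching about 60% at 9 months in that case under exponential weaning. So at least one half of the recommendation matters at either end of the effect range. The primary outcome and its sample size are untouched.

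**What to change.** Add a short paragraph to 3.1.12:

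- Compare time from birth to breastfeeding cessation between the randomised arms by Kaplan-Meier curves and a Cox model.
- Count women who never start as events at time zero, or at a small positive time if the software drops zeros.
- Censor women still breastfeeding at their last visit or at month 9.
- Adjust for breastfeeding intention at enrolment, named in advance and kept in the model whatever the observed balance.

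In 3.1.10, state that this adjustment is exempt from the rule based on observed imbalance. Intention is recorded before randomisation, so adjusting for it introduces no post-randomisation bias.

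The cost is a few lines of text. No new data, visits or participants are needed.
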